13.4.1.2. COWS, SOWS-Gossop, and SOWS-H

The treatment group difference for change in COWS, SOWS-Gossop, and SOWS-H total scores from Baseline to peak value and to each scheduled evaluation will be summarized descriptively with 95% confidence intervals. The treatment group differences will be calculated within the framework of analysis of covariance (ANCOVA) with treatment and total opioid dose (<90 MED, \geq 90 MED) as fixed factors and baseline score as a covariate.

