- ¹ Phone call will take place on Day 25, to check on the subject's well-being and to assess how the subject is feeling.
- ^m Phone calls will take place on Days 32, 39, and 46, to check on the subject's well-being and to assess how the subject is feeling.
- ⁿ Reminders contacts may be done via phone, text, or other electronic message. Remind the subjects about opioid dose reductions or, at Day 17, study drug dose reductions.
- Opioid dose will be decreased 50% from baseline MED beginning with the last dose of the day on Day -1, an additional 25% of baseline MED beginning on Day 6, and a final 25% (to dose of zero) beginning on Day 13. Opioid dose reduction may not occur on a Friday or Saturday unless the clinic can accommodate

subjects on Saturday and Sunday. Subjects who experience intolerable withdrawal symptoms despite increasing their dose of study drug to the maximum tolerated dose will be allowed to pause the opioid taper once. See Table 3 for the opioid taper schedule for subjects who must pause the taper.

- ^p Detailed study drug dosing information can be found in Section 9.2.3. Study drug taper begins on Day 18.
- ^q Subject interview will be conducted via a centralized interviewer through a phone call. The interview should take place no more than 5 days after the EOS Visit.
- ^r Training includes when to call the site due to symptoms of hypertension or hypotension, or if the subject records a vital signs measurement that meets the criteria to contact the site.
- ^s Training includes recording all pharmacologic and non-pharmacologic concomitant treatments (including opioid medications), study drug dose administration, scale assessments for both pain (Average Daily and Worst Daily NRS) and opioid withdrawal scales (SOWS-Gossop, SOWS-Handelsman, and MCGI-Subject), and recording of at-home vital signs (during study drug taper and through EOS only).

	Screeni	ing ^a							Study 1	Drug	Admi	nistra	tion ^b									Safety I	Follow-ı	ap
Method	Screenin g	RC	Visit 1	PC 1	Visit 2	RC		PC 2	Visit 3	RC		PC 3	Visit 4	RC		PC 3P	Visit 4P	RC	PC 4	Visit 5	PC 5	EOS	PCs 6,7,8	30-day PC 9
Timing	Days -28 to -2	Day -1	Day 1	Day 2	Day 3	Day 5	Day 6	Day 7	Day 8	Day 12	Day 13	Day 14	Day 15	Day 18	Day 19	Day 20	Day 21	Day 23	Days 24- 27	Day 28	Days 29- 33	Day 34		Follow -up ^c
Visit window					±1 day				±1 day				±1 day				±1 day			±1 day		±1 day		
Informed consent and HIPAA authorization	Х																							
Inclusion/exclusio n	Х																							

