Demographics	Х																							
Medical history	Х		updat e																					
Record Pain Management Plan	Х				•				Upd	ates sł	nould	be cap	tured t	hroug	hout	the stu	ıdy		I	•				
Characterize Baseline pain condition	Х																							
Characterize opioid use and opioid withdrawal history ^d	Х																							
MINI	Х																							
Randomization			Х																					
Complete PE	Х																							
Brief PE			Х		Х				Х				Х				Х			Х		Х		
Height	Х																							
Weight	Х																					Х		

Table 3:Schedule of Assessments Performed at the Clinic and Phone Calls: Study Schedule with Opioid Taper Pause

	Screen	ing ^a							Study]	Drug	Admi	nistra	tion ^b									Safety I	Follow-	սթ
Method	Screenin g	RC	Visit 1		Visit 2	RC		PC 2	Visit 3	RC		PC 3	Visit 4	RC		PC 3P	Visit 4P	RC	PC 4	Visit 5	PC 5	EOS	PCs 6,7,8	30-day PC 9
Timing	Days -28 to -2	Day -1	Day 1	Day 2	Day 3	Day 5	Day 6	Day 7	Day 8	Day 12	Day 13	Day 14	Day 15	Day 18	Day 19	Day 20	Day 21	Day 23	Days 24- 27	Day 28	Days 29- 33	Day 34	Days 35-56	Follow -up ^c
Visit window					±1 day				±1 day				±1 day				±1 day			±1 day		±1 day		
Urine pregnancy test ^e	Х																					Х		
Urine test for opioids	Х		X		x				Х				Х				Х			Х		Х		
Urine drug screen for illicit substances ^f	Х		x		х				X				X				X			х		Х		
Urine test for alcohol ^g	Х		Х		x				Х				Х				Х			х		Х		
Clinical chemistry	Х												Х									Х		
Hematology	Х																							
Urinalysis	Х																							
Vital signs ^h	Х		Х	Х	Х			Х	Х			Х	Х			Х	X			Х		Х		
Electrocardiogram	Х		Х		Х				Х				Х				X			Х		Х		
COWS			Х		Х				Х				Х				X			Х		Х		
SOWS-H and SOWS-Gossop			х		X				Х				Х				Х			Х		Х		
MCGI-S					Х				Х				Х				Х			Х		Х		
MCGI-R					X	1			Х				Х			1	Х	1		Х		Х		
NRS chronic pain scales	Х		x		x				Х				Х				х			Х		Х		X
NRS all over body pain scales			х		х				Х				Х				х			Х		Х		
EQ-5D-5L	Х																					Х		

	Screeni	ing ^a							Study]	Drug	Admi	nistra	tion ^b									Safety I	Follow-	սթ
Method	Screenin g	RC	Visit 1		Visit 2	RC		PC 2	Visit 3	RC		PC 3	Visit 4	RC		PC 3P	Visit 4P	RC	PC 4	Visit 5	PC 5	EOS	PCs 6,7,8	30-day PC 9
Timing	Days -28 to -2	Day -1	Day 1	Day 2	Day 3	Day 5	Day 6	Day 7	Day 8	Day 12	Day 13	Day 14	Day 15	Day 18	Day 19	Day 20	Day 21	Day 23	Days 24- 27	Day 28	Days 29- 33	Day 34	Days 35-56	Follow -up ^c
Visit window					±1 day				±1 day				±1 day				±1 day			±1 day		±1 day		
SF-36	Х																					Х		
ISI	Х												Х									Х		

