- ^s Training includes recording all pharmacologic and non-pharmacologic concomitant treatments (including opioid medications), study drug dose administration, scale assessments for both pain (Average Daily and Worst Daily NRS) and opioid withdrawal scales (SOWS-Gossop, SOWS-Handelsman, and MCGI-Subject), and recording of at-home vital signs (during study drug taper and through EOS only).

	Scree	ening								5	Study	Drug	g Adn	ninist	ratio	n ^a								Safety F	'ollow-up
Timing	Days -28 to -2	Day -1	Day 1	Day 2	Day 3	Day 4	Day 5	Day 6	Day 7	Day 8	Day 9	Day 10	Day 11	Day 12	Day 13	Day 14	Day 15	Day 16	Day 17	Day 18	Day 19	Day 20	Day 21	Days 22-27	Follow- up ^b
Site contact ^c		Х		Х			Х		Х					Х		Х			Х		Х			Х	Х
SOWS-H and SOWS-Gossop ^d			Х	Х	Х	Х	Х	Х	Х	Х	Х	Х	Х	Х	Х	Х	Х	Х	Х	Х	Х	Х	Х	Х	
MCGI-S ^d			Х	Х	Х	Х	Х	Х	Х	Х	Х	Х	Х	Х	Х	Х	Х	Х	Х	Х	Х	Х	Х	Х	
NRS chronic pain scales ^{d,e}	Х	Х	Х	Х	Х	Х	Х	Х	Х	Х	Х	Х	Х	Х	Х	Х	Х	Х	Х	Х	Х	Х	Х	Х	X
NRS all over body pain scales ^d			Х	Х	Х	Х	X	Х	Х	Х	Х	Х	Х	Х	Х	Х	Х	Х	Х	Х	Х	Х	Х	Х	
EQ-5D-5L																									Х
Record study drug and concomitant treatment use ^d		Х	X	X	X	X	X	X	X	Х	Х	Х	X	X	Х	X	X	X	X	X	Х	Х	Х	х	
Vital signs – Phone report ^f				Х					Х							Х									
Vital signs – Subject diary ^g																				Х	Х	Х	Х	Х	
AEs				Х					Х							Х									Х

Table 4: Schedule of Assessments Performed at Home: Standard Study Schedule

AE = adverse event; EOS = end of study; EQ-5D-5L = EuroQol 5-Dimension 5-Level; MCGI-S = Modified Clinical Global Impression – Subject Version; NRS = Numeric Rating Scale; SOWS-Gossop = Short Opiate Withdrawal Scale of Gossop; SOWS-H = Subjective Opiate Withdrawal Scale of Handelsman

^a Subjects who experience intolerable withdrawal symptoms may temporarily suspend the opioid taper once (Section 9.3). See study drug taper schedule (Section 9.2.3). See Table 5 for the schedule of assessments to be performed at home for subjects who must pause the taper.

^b Phone call 30 days after the last dose of study drug. Subjects will be asked to report their current opioid dose/regimen and complete several scales (EQ-5D-5L and NRS pain scales) over the phone.

^c Reminder contacts will take place on Days -1, 5, 12, and 17. Phone calls from the clinic staff will take place on Days 2, 7, 14, 25, 32, 39, 46, and 30 days following the last dose of study drug (follow-up phone call). A subject phone interview, conducted by a centralized interviewer, will take place between Days 28 and 33.

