^d Completed at home before bedtime.

^e Subjects will continue to complete the NRS chronic pain scales every day between the EOS Visit and the phone call 30 days following the last dose of study drug (follow-up phone call).

^f During the phone call to the subject, the site should ask the subject to collect and report their vital signs. The subject will not record this reading in their diary.

^g Readings will be taken once in the morning and once in the evening and reported in the subject's diary.

	Scree	ning											Stu	ıdy E	Drug	Adn	ninis	trati	i on a												afety low-up
Timing	Days -28 to -2	Day -1		Day 2	Day 3	Day 4	Day 5	Day 6	Day 7	Day 8	Day 9	Day 10	Day 11	Day 12	Day 13				Day 17	Day 18				Day 22	Day 23	Day 24	Day 25			Days 28- 33	Follow- up ^b
Site contact ^c		Х		Х			Х		Х					Х		Х				Х		Х			Х		Х			Х	Х
SOWS-H and SOWS-Gossop ^d			X	х	х	х	Х	х	х	Х	х	х	Х	х	х	Х	х	х	х	Х	х	х	х	х	х	х	х	х	х	Х	
MCGI-S ^d			Х	Х	Х	Х	Х	Х	Х	Х	Х	Х	Х	Х	Х	Х	Х	Х	Х	Х	Х	Х	Х	Х	Х	Х	Х	Х	Х	Х	
NRS chronic pain scales ^{d,e}	Х	Х	х	х	х	х	Х	х	х	Х	х	х	х	х	Х	Х	х	х	х	Х	х	х	х	х	х	х	х	Х	Х	Х	Х
NRS all over body pain scales ^d			Х	х	х	х	Х	х	х	Х	Х	х	х	х	Х	Х	х	х	х	Х	Х	х	х	х	Х	х	х	Х	Х	Х	
EQ-5D-5L																															Х
Record study drug and concomitant treatment use ^d		X	x	x	x	x	х	x	х	х	x	х	x	х	х	х	x	x	x	х	x	х	x	x	x	x	x	Х	Х	Х	
Vital signs – Phone report ^f				х					Х							Х						Х									
Vital signs – Subject diary ^g																										х	х	Х	Х	Х	
AEs				Х					Х							Х						Х									Х

Table 5: Schedule of Assessments Performed at Home: Study Schedule with Opioid Taper Pause

AE = adverse event; EOS = end of study; EQ-5D-5L = EuroQol 5-Dimension 5-Level; MCGI-S = Modified Clinical Global Impression – Subject Version;

NRS = Numeric Rating Scale; SOWS-Gossop = Short Opiate Withdrawal Scale of Gossop; SOWS-H = Subjective Opiate Withdrawal Scale of Handelsman ^a Subjects who experience intolerable withdrawal symptoms may temporarily suspend the opioid taper once (Section 9.3). See study drug taper schedule (Section 9.2.3).

^b Phone call 30 days after the last dose of study drug. Subjects will be asked to report their current opioid dose/regimen and complete several scales (EQ-5D-5L and NRS pain scales) over the phone.

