7.2.2. Effectiveness Endpoints

The following effectiveness endpoints will assess withdrawal symptoms and pain:

- Percentage of subjects who successfully complete each scheduled dose reduction and the opioid taper to complete opioid discontinuation, with or without a pause.
- Change in COWS from Baseline to peak value and to each scheduled evaluation.
- Change in SOWS-H from Baseline to peak value and to each scheduled evaluation.
- Change in SOWS-Gossop from Baseline to peak value and to each scheduled evaluation.
- Modified Clinical Global Impression Rater Version (MCGI-R) by each scheduled evaluation.
- Modified Clinical Global Impression Subject Version (MCGI-S) by each scheduled evaluation.
- Time to study drug discontinuation.
- Change in daily opioid dose, expressed as MED, and as a percentage of the baseline MED.
- Number of non-opioid concomitant medications for withdrawal symptoms used by study day.
- Change in average and worst daily pain from Baseline to peak value as measured by the Numeric Rating Scale (NRS).
- Change in EuroQol 5-Dimension 5-Level (EQ-5D-5L) scale from Baseline to each scheduled evaluation.
- Change in Short Form Health Survey 36 Items (SF-36) scale from Baseline to each scheduled evaluation.
- Change in Insomnia Severity Index (ISI) from Baseline to each scheduled evaluation.
- Change in Hospital Anxiety and Depression Scale (HADS) from Baseline to each scheduled evaluation.

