Non-opioid medications taken during the study should be in compliance with the allowed concomitant treatments in Section 9.4. Opioid dose reductions may not occur on a Friday or Saturday unless clinic can accommodate subjects on Saturday and Sunday. Qualified study personnel at the clinic should call the subject the day after the opioid dose is decreased (except on Day 1 since the subject will come to the clinic) to review the subject's at-home vital signs measurement and how the subject is feeling. Upon review by the Investigator or designee, changes to dosing of study drug should also be discussed with the subject, if applicable.

Subjects who experience intolerable withdrawal symptoms despite increasing their dose of study drug to the maximum tolerated dose (not to exceed 4 tablets QID) will be allowed to pause the opioid taper once. Pausing the opioid taper includes either a return to the last stable opioid dose for the remainder of the current opioid dose reduction period, or remaining on the current opioid dose instead of reducing at the next scheduled reduction, resulting in an overall extended opioid taper period and study duration. For example, if a subject experiences intolerable withdrawal at the second opioid dose reduction step [25% of baseline MED], they may either 1) return to the first reduction dose [50% of baseline MED]) or, 2) when the withdrawal persists until the next scheduled reduction step, they may remain for longer at the current opioid dose [25% of baseline MED]. In both cases, the taper must be resumed following the single pause in accordance with the protocol schedule. Subjects who cannot or are unwilling to continue the opioid taper after one pause will be discontinued from the study.

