Decisions on whether to pause the opioid taper will be based on subject request and an evaluation (in clinic or over the phone) of the subject's status by the Investigator. Subjects may request to pause the opioid taper due to opioid withdrawal symptoms. If the subject's last COWS score is \geq 5 OR if based on i) the Investigator's discussion with the subject, ii) review of ongoing subject-reported withdrawal related AEs, and iii) most recent scores for subject reported withdrawal scales, the subject's desire to pause the taper is related primarily to opioid withdrawal discomfort in the Investigator's desire to pause the taper may be paused. In the event that the Investigator assesses the subject's desire to pause the taper to be primarily related to pain, a taper pause will not be permitted; however, if the subject is willing to continue the per protocol taper, recommended modifications to their concurrent pain management plan should be discussed and recorded. Subjects unwilling to continue the per protocol taper and not experiencing opioid withdrawal to permit a single pause should be discontinued from the study.

Study drug dosing for an opioid taper pause will remain at the discretion of the Investigator, as guided by subject tolerability of study drug and opioid withdrawal symptoms. The dose of study drug can be increased or decreased as needed.

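### Minor: Section 13.4.1.2 does not exclude Visit 4P, which only subjects who paused the taper attend, from its between-group contrasts, and Section 13.4.1.4 names no strata for the log-rank test.

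*Combined protocol and SAP*

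**What the plan says.** Section 13.4.1.2 covers "The treatment group difference for change in COWS, SOWS-Gossop, and SOWS-H total scores from Baseline to peak value and to each scheduled evaluation", estimated by ANCOVA with treatment, MED stratum and baseline score. The Synopsis adds that differences in mean change will also be tested in that model. Section 7.2.2 uses the same timing for the global impression scales, for example "Modified Clinical Global Impression Rater Version (MCGI-R) by each scheduled evaluation", and Section 13.4.1.3 analyses both of them by a stratified CMH test.

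Section 3.3 has two clinic schedules. Visit 4P (Day 21), with COWS, both SOWS scales and both global impression scales marked, is a column only in Table 3, "Schedule of Assessments Performed at the Clinic and Phone Calls: Study Schedule with Opioid Taper Pause". Table 2 goes from Visit 4 (Day 15) to Visit 5 (Day 22). There are also two home schedules. Table 4, "Schedule of Assessments Performed at Home: Standard Study Schedule", ends its diary with Days 22-27. Table 5, "Schedule of Assessments Performed at Home: Study Schedule with Opioid Taper Pause", ends with Days 28-33.

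Section 9.3 limits the pause to "Subjects who experience intolerable withdrawal symptoms despite increasing their dose of study drug to the maximum tolerated dose".

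Section 9.1.1 stratifies randomization by <90/≥90 MED. Section 13.4.1.4 stratifies the Kaplan-Meier curve by the same factor, then names the log-rank test without strata. Section 13.1 calls Section 13 an overview and leaves details to a statistical analysis plan, to be final before database lock.

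**The concern.** Taken at its word, Section 13.4.1.2 yields an arm difference at Visit 4P. Everyone with a value there was selected after randomization by the severity of withdrawal, which the drug is meant to reduce. If it does so, fewer lofexidine subjects pause, and those who do are the more severe part of their arm. An ANCOVA on the two selected groups would look like a randomized result without being one. The study is a pilot meant to inform a pivotal design, so a weakened estimate from such a table could be carried forward.

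The log-rank point is separate. Leaving the strata open allows two p-values from the same 60 subjects. If the strata predict stopping, the unstratified test after stratified randomization is conservative and loses power.

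**Working it through.** **1. Which timepoints belong only to pausers.**
- Visit 4P: Table 3 only.
- Day 28: not pauser-only. Standard-schedule subjects have clinic scores at EOS that day (Table 2), while pausers are at Visit 5 (Table 3). A contrast by calendar day would mix two stages of the taper.
- Days 29-33: diary values in Table 5 only, apart from a standard-schedule EOS visit falling on Day 29 under the ±1 day window. This concerns the SOWS scales and MCGI-S; COWS and MCGI-R are clinic-only.

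**2. Whether common visit labels solve the problem.** Table 2 puts the last opioid step, "and a final 25% (to dose of zero) beginning on Day 13". Table 3 puts it on Day 19. Days from that step:
- Visit 5: 22 − 13 = 9 and 28 − 19 = 9.
- EOS: 28 − 13 = 15 and 34 − 19 = 15.
- Visit 4: 15 − 13 = 2 on the standard schedule, and 15 − 19 = −4 for subjects who paused earlier.

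Visits 2, 3, 4, 5 and EOS are on both schedules, so contrasts by label are open to all randomized subjects still attending. Visit 5 and EOS also match by taper stage.

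**3. Size at Visit 4P (all inputs assumed).** SOWS-Gossop SD 6; drug effect −3 before the pause; subjects pause above one severity cut; 40% of placebo pause.
- Cut in placebo SD units: 0.253. In lofexidine SD units: 0.253 + 3/6 = 0.753, so 23% pause. With 30 per arm, that is about 12 against 7 subjects.
- Shift = correlation × 6 × [λ(0.753) − λ(0.253)], with λ the normal hazard: correlation × 6 × (1.331 − 0.966) = correlation × 2.19.
- At a correlation of 0.3, 0.5 or 0.7 between severity at the pause and the Visit 4P score, the shift is 0.66, 1.10 or 1.53 points against lofexidine. A true −3 reads −2.3, −1.9 or −1.5.
- Baseline adjustment reduces the shift without removing it: 0.49, 0.95 and 1.45 at a baseline correlation of 0.3; 0.13, 0.66 and 1.18 at 0.5.
- 95% half-width: t(17) × 6 × √(1/12 + 1/7) = 2.11 × 6 × 0.476 = 6.0.
- If the drug does nothing, the shift is 0.

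A second simulation, in SD units and with baseline in the model, points the same way: an effect of −0.30 in all randomized subjects becomes −0.07 to −0.10 among pausers.

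With pause rates from 10%/10% to 50%/30% (placebo/lofexidine), Visit 4P would hold 6 to 24 subjects. The four-parameter ANCOVA would then have 2 to 20 residual degrees of freedom.

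**4. Log-rank test (all inputs assumed).** 30 per arm, two equal strata balanced by arm, exponential premature stops, everyone censored at Day 21, treatment hazard ratio 0.4, placebo completion 45%; 55% completion in the null runs; 5000 trials per setting.

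| Stratum hazard ratio | Power, unstratified | Power, stratified | Null rejection, unstratified | Null rejection, stratified |
|---|---|---|---|---|
| 1 | 60% | 60% | 5.0% | 5.0% |
| 2 | 59% | 60% | 4.4% | 5.2% |
| 3 | 55% | 61% | 3.5% | 5.0% |
| 5 | 50% | 63% | 2.6% | 5.0% |

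A separate run gave 55% against 60% at a ratio of 3 and 52% against 63% at 5. Across both runs the gain is about 5 to 13 points.

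**The case against.** The strongest reply is that Section 13 is expressly an overview. Handling an optional visit and naming test strata are the details it leaves to the later plan, and silence does not show that a wrong analysis is intended. A sensible analyst would use the common visit labels anyway. That is fair and keeps the point minor. It does not remove it: deferral supplies no rule, and the present wording, followed literally, includes Visit 4P.

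The second reply, that the effects are small and every input is assumed, also stands in part. The Visit 4P shift is well inside its own confidence interval, and under this model it runs against lofexidine, so it would not create a false benefit.

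A reader might infer more than the documents support:
- That the plan specifies an unstratified log-rank test. It is silent, and the sentence before stratifies the curve.
- That Type I error is inflated. In the table above, the unstratified test is conservative.
- That the whole Days 28-33 diary block is pauser-only. Day 28 is not.
- That the pause seriously distorts Visit 4 or the peak scores. Under assumed inputs, pausers still being on opioid at Visit 4 shifts the contrast by 0 at equal pause rates, 0.2 to 0.6 points at 30% against 20%, and 0.4 to 1.2 at 40% against 20%; the half-width is 2.6 to 3.1. Pausers' extra chances to peak add under 0.1 point between arms at a within-subject SD of 4 and a 20-point difference in pause rates.

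**Conclusion.** Both parts hold as minor points about secondary analyses; the primary safety objective is untouched. That a Visit 4P contrast is not randomized follows from Tables 2 and 3 and the pause rule in Section 9.3, with no numerical assumption. Its size, roughly 0.7 to 1.5 points before baseline adjustment, rests on the assumed SD, pause rates and correlations, and is zero if the drug has no effect. The diary part applies to Days 29-33 and only if diary days are scheduled evaluations. The value of log-rank stratification depends on whether MED predicts stopping, on which the documents give no figures: nothing at a stratum hazard ratio of 1, about 5 to 13 points of power at 3 to 5.

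**What to change.** In the statistical analysis plan, before database lock:

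1. For Sections 13.4.1.2 and 13.4.1.3, compare all ITT subjects by common visit label (Visits 2, 3, 4, 5, EOS). Make no between-group contrast or test at Visit 4P or on pauser-only diary days; list or describe those data by arm. Tabulate pauses by arm and taper step.
2. For Section 13.4.1.4, state that the log-rank test is stratified by <90/≥90 MED. If a censoring day is specified, use one common cut-off, Day 21, for all subjects. Censoring completers at Day 21 or Day 27 according to schedule would leave only pausers at risk on Days 22-27, and so repeat the problem in (1). The common cut-off leaves out any stops by pausers after Day 21.

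A supportive contrast about 2 days after the zero-opioid step (Visit 4, or Visit 4P for pausers) is optional and not needed here. If wanted, define it by pause status, not by being at zero opioid at Visit 4, so that non-pausers who took rescue opioid keep their Visit 4 value.

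The cost is a few sentences and one table from data already collected. Stratifying gains nothing if MED does not predict stopping.

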8.5. Subject Discontinuation Criteria

The Investigator or Sponsor may discontinue individual subjects from the study at any time if it is deemed clinically appropriate or for any reason, including the following:

- Cardiovascular events
 - QTcF >500 msec or >25% above screening value for both males and females.
 - New onset of clinically significant abnormal electrocardiogram (eg, second- or third-degree heart block or uncontrolled arrhythmia, prolonged QTcF interval).
 - Persistent signs or symptoms of hypotension, bradycardia, or hypoperfusion.

- Single occurrence of symptomatic bradycardia (as assessed by the Investigator, regardless of blood pressure) associated with chest pain, shortness of breath, or decreased level of consciousness.
- Medical intervention for cardiovascular event: Any medical intervention (nonmedication or medication inclusive) used for the treatment of any cardiovascular event, with the exception of a positional intervention in subjects displaying hypotension.
- Any other clinically significant cardiovascular signs or symptoms that would place the subject at risk.
- Evidence of repeated alcohol use (eg, 2 positive alcohol tests after Screening) during the study. Alcohol or other sedative/hypnotic withdrawal signs and symptoms developing following enrollment into the study.
- More than 2 repeat occurrences of opioid rescue medication usage reported by the subject after Screening.
- An intolerable AE or SAE; the relationship to study drug must be recorded in source.
- Requirement for a treatment that is prohibited (Section 9.4) by the protocol.
- Noncompliance with the protocol, including but not limited to showing evidence of illicit drug use while participating in the study or refusal or inability to continue opioid taper schedule per protocol.
- Lost to follow up: If a subject is lost to follow-up, repeated attempts (defined as a minimum of 3 telephone calls, followed by sending a letter) will be made to reach the subject. If repeated attempts are unsuccessful, lost to follow up will be recorded in the subject's source document and electronic case report form (eCRF) as the reason for early discontinuation.

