8.6. Early Discontinuation Visit

If a subject is discontinued from the study before completion, regardless of whether they have received study drug, the reason for discontinuation must be documented in the subject's source document and eCRF. Whenever a subject is discontinued, the procedures/assessments listed for the EOS Visit in the Schedule of Assessments (Table 2 or Table 3) should be performed. If a subject discontinues on a scheduled visit, assessments completed at that visit should be entered into the eCRF for that scheduled visit. Assessments required for the EOS Visit that are not required at the scheduled visit (eg, a complete physical examination, clinical laboratory tests) should be completed and entered into the eCRF for the EOS Visit.

Subjects who prematurely discontinue the study will be instructed to taper study drug as described in Section 9.2.3 and to complete the at-home assessments for the study drug taper period (Table 4 or Table 5). Once discontinued, subjects may not re-enter the study.

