- Nonsteroidal anti-inflammatory drugs provided dosing is within product label recommendations
- Non-opioid topical treatments (compounded or non-compounded)
- Non-prescription medications that are often taken to treat pain, depression and anxiety (excluding St. John's Wort, Kratom, cannabis and products containing cannabinoids)
- Non-pharmacologic modalities/interventions (eg, physical therapy, psychotherapy, hypnosis, acupuncture, massage, chiropracty, ice packs, moist or dry heat, etc)

Use of opioid medication as a rescue for breakthrough pain should be strongly discouraged. Subjects experiencing intolerable pain during the study should be instructed to call the site to discuss further modifications to their non-opioid pain management plan. Subject reported use of any opioid rescue medication should be recorded and discussed by the Investigator and Medical Monitor to assess eligibility to continue in the study and will include a review of safety concerns, impact on effectiveness measures, and consistency with required MED-percent reduction targets. More than 2 repeat occurrences of opioid rescue medication usage reported by the subject will require study discontinuation.

Use of any medication or non-pharmacologic intervention or treatment for pain will be recorded daily by subjects using the diary.

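### The withdrawal-scale ANCOVAs state no handling of missing visits, although the protocol forces withdrawal-related discontinuation, so late-visit contrasts and peak can be biased

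*Combined protocol and SAP*

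**What the plan says.** Section 7.2.2 lists "Change in COWS from Baseline to peak value and to each scheduled evaluation" as an effectiveness endpoint, with matching endpoints for SOWS-H and SOWS-Gossop. Section 13.4.1.2 says that the change "from Baseline to peak value and to each scheduled evaluation will be summarized descriptively with 95% confidence intervals", and then: "The treatment group differences will be calculated within the framework of analysis of covariance (ANCOVA) with treatment and total opioid dose". Baseline score is the covariate. No repeated-measures model, imputation, estimand or sensitivity analysis is named. The only missing-data rule in Section 13 concerns blank SF-36 items (Section 13.4.1.6).

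Section 9.3 states: "Subjects who cannot or are unwilling to continue the opioid taper after one pause will be discontinued from the study". Section 9.4.2 adds: "More than 2 repeat occurrences of opioid rescue medication usage reported by the subject will require study discontinuation". Section 8.5 lists other grounds, among them "Persistent signs or symptoms of hypotension, bradycardia, or hypoperfusion".

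Some data are kept when a subject leaves. Section 8.6 says: "Whenever a subject is discontinued, the procedures/assessments listed for the EOS Visit in the Schedule of Assessments (Table 2 or Table 3) should be performed". Those procedures include COWS and both SOWS scales. The subject is also asked to fill in the home diary while study drug is tapered. No withdrawal scale is scheduled after that.

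**The concern.** The protocol takes subjects out of the study because of the outcome that these scales measure. If a Day 15 or Day 22 contrast is fitted by itself, it compares those who are left, and a leaver's earlier scores do not inform that contrast. If more subjects with severe withdrawal leave placebo than active, the remaining placebo group looks better than the randomised group would have.

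Peak has a different problem. It is a maximum over whatever assessments a subject has, so it tends to rise with their number. Early leavers have few. A pause, which is itself granted for withdrawal symptoms, adds a clinic visit and six diary days.

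Estimating these differences is a secondary objective, and the synopsis says that the pilot is meant to inform the design of a pivotal study. A biased estimate would carry over into that design.

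**Working it through.** **The plan's own figure.** The only precision statement (Section 13.2) concerns a difference in proportions, not these scales. It reproduces with 0.10 vs 0.30: 1.96 × sqrt(0.10×0.90/n + 0.30×0.70/n) gives 0.240 at n = 20 and 0.170 at n = 40. The plan gives no precision figure for the withdrawal scales.

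**Assessments behind peak COWS.** The Day 1 COWS is taken before dosing and serves as baseline. Table 2 then has Days 3, 8, 15, 22 and 28, which is 5 visits. Table 3 has Days 3, 8, 15, 21, 28 and 34, which is 6. The diary runs to Day 27 in Table 4 and Day 33 in Table 5. For equal-mean normal scores the expected maximum is sqrt(1 - correlation) × the independent-normal value. That value is 1.16 SD for 5 and 1.27 SD for 6. At correlation 0.5 the results are 0.82 and 0.90 SD. One extra visit is therefore worth about 0.1 SD.

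**Bias, first simulation.** Every input is an assumption: scores at Days 1, 3, 8, 15 and 22, SD 6, correlation 0.6, true effect up to 3 points, 200,000 per arm. After each visit a subject leaves with probability 0.3 to 0.6 if the score is above a threshold (12 to 18), otherwise 0.02. Negative means benefit. The MAR column is sequential-regression imputation that uses earlier visits.

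| Dropout mechanism | Dropout by Day 22, placebo / active | Day 22: full data / present only / MAR | Peak: full data / observed |
|---|---|---|---|
| Score-driven, lightest | 12% / 9% | -2.57 / -2.46 / -2.58 | -2.68 / -2.61 |
| Score-driven, heaviest | 47% / 32% | -2.58 / -2.10 / -2.66 | -2.72 / -2.29 |
| Triggering score not recorded | 31% / 20% | -2.58 / -2.12 / -2.28 | -2.70 / -1.97 |
| Score-driven, plus 5% AE dropout per visit on active | 27% / 29% | -2.56 / -2.28 / -2.60 | -2.70 / -2.88 |
| Score-driven, plus 20% AE dropout per visit on active | 27% / 58% | -2.56 / -2.27 / -2.62 | -2.70 / -3.88 |
| No true effect, 10% AE dropout per visit on active | 27% / 47% | -0.01 / -0.02 / -0.01 | 0.01 / -0.85 |
| No true effect, equal dropout | 27% / 27% | 0.00 / -0.01 / -0.01 | -0.01 / -0.01 |

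- By visit, score-driven dropout: 1 - 2.46/2.57 = 4% to 1 - 2.10/2.58 = 19% shrinkage.
- Peak, score-driven dropout: 1 - 2.61/2.68 = 3% to 1 - 2.29/2.72 = 16% shrinkage. It is 1 - 1.97/2.70 = 27% if the triggering score is missed.
- Peak with AE dropout on active: 2.88/2.70 - 1 = 7% to 3.88/2.70 - 1 = 44% inflation.
- If AE dropout on active falls only on low scorers, the Day 22 effect is -2.01 against -2.59, a 22% shrinkage; MAR gives -2.63.

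**Bias, second simulation.** Assumed between-subject SD 3, residual SD 2.5, true effect 3.0, dropout logistic in the Day 8 score. The present-only estimate was 2.73 at 38% vs 18% dropout, 2.82 at 27% vs 11%, and 2.90 at 11% vs 3%. That is 9%, 6% and 3% shrinkage. Using earlier visits gave 2.99 to 3.02. Taken together, the by-visit range under score-driven dropout is roughly 3 to 19%.

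**Against sampling error.** At 30 per arm the 95% half-width for a mean difference is 1.96 × sqrt(2/30) = 0.51 SD, or about 3.0 points at SD 6. Baseline adjustment at correlation 0.6 multiplies this by sqrt(1 - 0.36) = 0.8, giving about 2.4. The largest score-driven by-visit bias is 2.58 - 2.10 = 0.48 points.

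**The case against.** Section 13.1 calls the section an overview and leaves detail to a separate SAP that is not in the text supplied. A reader might infer that the plan prescribes an analysis of observed cases only. It does not say so; that is a reading of its silence. The silence still matters. The SAP need only be final before database lock, while Section 9.1.2 unblinds programmers and sponsor-designated reviewers after about 30 subjects, so the rule could be set after an unblinded look.

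A reader might also infer that leavers' scores are discarded or that dropout is ignored. Neither is supported. Those scores enter the visits attended and the peak, Section 8.6 collects the scales at discontinuation, and taper completion and time to study drug discontinuation are analysed in their own right. What is missing is a rule for how a discontinuation assessment enters the Day 15 or Day 22 contrast. If it is filed as end of study, that contrast mixes early leavers with subjects at Day 28 or 34.

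Two further objections stand. This is a pilot with safety as its primary objective, and the likely bias is below its sampling error. The recovery under MAR is also partly built in, because dropout was made to depend on recorded scores; where the triggering score was missing, MAR gave only -2.28 against -2.58.

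**Conclusion.** The point holds as a gap in the analysis plan. Section 13.4.1.2 states no handling of missing visits for outcomes that themselves lead to discontinuation. Under score-driven dropout the by-visit effect shrinks by roughly 3 to 19%, which is smaller than the sampling error at 30 per arm. For peak, the direction is open.

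A reader might conclude that the plan understates the drug's benefit. The documents do not support that as a general statement. By-visit shrinkage needs a true benefit and withdrawal-driven dropout that is heavier on placebo. For peak, adverse-event dropout on active shortens observation and can inflate the benefit or produce one where none exists. Pausers' extra assessments could also raise peaks on placebo if pauses are more frequent there.

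All sizes rest on assumed SDs, correlations, effects and dropout rates, because the documents give none. The consequence is for secondary estimates used to plan a later trial. The change is worth making because it is cheap and needs weaker missing-data assumptions.

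**What to change.** Replace the by-visit ANCOVAs with one repeated-measures model for each scale: treatment, visit, treatment-by-visit, MED stratum, baseline and baseline-by-visit, fitted to all post-baseline data, with visit contrasts and 95% confidence intervals. Assign the early-discontinuation assessment to the visit nearest its actual study day, and state where the additional visit of the pause schedule falls. Say in one sentence what the contrast estimates for subjects who stop.

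Add one sensitivity analysis for dropout that recorded scores do not explain. Report peak descriptively, with the number of contributing assessments per arm. A mean daily score over the days observed would not replace these steps, because it is also cut short by informative dropout. Fix the wording before the unblinded interim analysis.

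The cost is slightly more programming, a pre-stated simpler covariance structure in case the model does not converge, and reliance on a missing-at-random assumption in the main analysis.
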